#### 7.2.1 Safety Analyses

Not applicable

# 7.2.2 Analyses of endpoint

The following tables and figures will be generated for the analysis of endpoints.

- 1. The distribution of demographics characteristics (mean ±SD for age and frequency and percentage for sex)
- 2. MRD negativity following initiation of InO (frequency and percentage)
- 3. Dosage pattern (frequency and percentage)
- 4. Cause of death (frequency and percentage)
- 5. Occurrence of Grade 3/4 treatment-related adverse events in lung/cardiac/kidney/liver etcfollowing InO initiation (frequency and percentage)
- 6. CR/CRi in EMD/LBL (frequency and percentage)
- 7. Duration of response (DOR) (Median and Interquartile Range (IQR))
- 8. No of patients who proceeded to transplant (Median and IQR)
- 9. Total during study treatment and post HSCT (Median and IQR)
- 10. Restricted remission free time with 95% confidence interval for both complete remission and complete remission with incomplete hematological recovery.

- 11. Restricted remission free time with 95% confidence interval for both complete remission and complete remission with incomplete hematological recovery stratified by the number of salvage therapies  $(0, 1, \ge 2)$  received before InO initiation
- 12. Restricted mean overall survival time with 95% CI.
- 13. Restricted relapse-free-survival with 95% CI for all patients and patients with or without follow-up HSCT.

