#### 9.5. Data analysis

All qualitative outcomes will be summarized by frequency and percentage. The quantitative outcome will be summarized by mean and SD if data is symmetric, otherwise median, and IQR. The outcomes will also be classified and compared across different demographic and relevant clinical factors. External validity will be assessed by t-test/ANOVA or chi-square test of indepdence depending on the nature of the outcome. However, observations will be generalized for the population the selected patients would represent. p-value<0.05 will be considered statistical significance. A standard statistical software will be used for data analysis.

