#### 9.7. Limitations of the research methods

- The medical records may not be available for each & every data points provided in the CRF, from the aspect of the clinician or the patient.
- Patients may be lost to follow-up due to the occurrence of AEs, lack of efficacy or other reasons.
- This could be due to censoring events, that is, information on time to outcome event may not available for all study participants. Patient/s in such cases will be marked as "censored" when such information on time to event is not available due to loss to follow-up or non-occurrence of outcome events before the end of the study.
- For such patients (censored because of lost to follow-up due to the occurrence of AEs, lack of efficacy or other reasons), the use of Kaplan-Meier curves will be obtained as estimates of median OS, RFS and time to CR/Cri taking into account patients' attrition.
- The interpretation of data collected retrospectively will be dependent on the completeness and quality of the medical records and the reliability of the abstraction of data from the medical records. However, Source data verification (SDV) will be employed to identify and correct abstraction errors.

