# 6 HANDLING OF MISSING VALUES

Owing to the descriptive nature of the study, analysis will be on available data only. No imputation of missing data will be implemented.

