# 7.2 STATISTICAL ANALYSES

The distribution demographics variables like age and sex will be summarized by mean  $\pm$ SD and frequency (%) respectively. The prevalence of complete remission or complete remission with incomplete hematological recovery following treatment with InO will be reported with 95% confidence interval. Further these prevalence will be estimated for the

number of salvage therapies  $(0, 1, \ge 2)$  received before InO initiation.6 months or 12 months restricted mean remission free time will be estimated with 95% CI for both complete remission or complete remission with incomplete hematological recovery. The Kaplan-Meier curves of remission free survival will be drawn if a sufficient representation observed across the number of salvage therapies  $(0, 1, \ge 2)$  received before InO initiation. The restricted mean remission free time with 95% CI will be estimated for categories of number of salvage therapies. Restricted mean/median survival time will also be estimated with 95% CI. The Kaplan-Meier overall survival curve will also be drawn.

Other secondary endpoints like MRD negativity following initiation of InO or dosage pattern, concomitant medications, cause of death , occurrence of Grade 3/4 treatment-related adverse events in lung/cardiac/kidney/liver etc. following InO initiation and CR/CRi in EMD/LBL will also summarized by frequency and percentage and dration of response(DOR), no of patients who proceeded to transplant, total during study treatment and post HSCT will be summarized my median and interquartile range. restricted relapse-free-survival time will also be estimated with 95% CI if data permits for all patients and patients with or without follow-up HSCT.

Due to non-probability sampling technique, the extrapolation of the results will be restricted to the population that matches with sample characteristics only. Magnitude of the measure of any characteristics will be prioritised over statistical interpretation. However, interpretation of the result will be in a qualitative sense even though the related feature is compared numerically owing to descriptive nature of the study.

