#### List of figure

- 1. Kaplan-Meier curve for remission free survival
- 2. Kaplan-Meier curve for remission free survival stratified by the number of salvage therapies (0, 1, ≥2) received before InO initiation
- 3. Kaplan-Meier survival curve for overall survival

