#### 8 LIST OF TABLES AND TABLE SHELLS

- 1. The distribution of demographics characteristics (mean±SD for age and frequency and percentage for sex)
- 2. MRD Negativity following initiation of InO(frequency and percentage)
- 3. Dosage pattern(frequency and percentage)
- 4. Cause of death (frequency and percentage)
- 5. Occurrence of Grade 3/4 treatment-related adverse events in lung/cardiac/kidney/liver etc following InO initiation (frequency and percentage)
- 6. CR/CRi in EMD/LBL (frequency and percentage)
- 7. Duration of response(DOR) (Median and IQR)
- 8. No of patients who proceeded to transplant (Median and IQR)
- 9. Total during study treatment and post HSCT (Median and IQR)
- 10. Restricted remission free time with 95% confidence interval for both complete remission and complete remission with incomplete hematological recovery.
- 11. Restricted remission free time with 95% confidence interval for both complete remission and complete remission with incomplete hematological recovery stratified by the number of salvage therapies  $(0, 1, \ge 2)$  received before InO initiation
- 12. Restricted mean overall survival time with 95% CI.
- 13. Restricted relapse-free-survival with 95% CI for all patients and patients with or without follow-up HSCT

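### Duration of remission is given an ordinary median and IQR and is on no Kaplan-Meier list, so the plan has no valid way to handle remissions still running at last contact

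*SAP*

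**What the plan says.** DOR is one of twelve secondary endpoints (Protocol 9.1.4; SAP section 5). Three places in the SAP fix its summary:

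- Section 7.2.2, item 7: "Duration of response (DOR) (Median and Interquartile Range (IQR".
- Section 8, item 7: "Duration of response(DOR) (Median and IQR".
- Section 7.2, text: DOR shares a clause with the number of patients transplanted and a total on treatment and after transplant. The clause ends "post HSCT will be summarized my median and interquartile range".

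None of these gives a censoring rule, a confidence interval or a count of censored patients. The SAP appendices on derivations and further endpoint definitions are empty.

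Censored methods appear elsewhere in the plan. Protocol 9.7 expects loss to follow-up and non-occurrence of events before study end, marks such patients as censored, and states that "the use of Kaplan-Meier curves will be obtained as estimates of median OS, RFS and time to CR/Cri". DOR is not named. The SAP figure list has "Kaplan-Meier curve for remission free survival", the same curve by number of prior salvage therapies, and "Kaplan-Meier survival curve for overall survival". SAP 7.1 adds a curve for relapse-free survival. DOR is in none of these.

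The general rule in Protocol 9.5 is "The quantitative outcome will be summarized by mean and SD if data is symmetric, otherwise median, and IQR". SAP 5.1 currently measures duration of remission as the time from starting InO to reaching CR/CRi.

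**The concern.** Duration of remission is a time-to-event quantity. A responder still in remission at data extraction, or lost while in remission, has a known minimum duration but no end date. An ordinary median and IQR cannot use that information. The analyst must omit the patient, which leaves only remissions that ended, or enter the time to last contact as if the remission had stopped there. The longest remissions are the likeliest to be unfinished, so both routes pull the summary down.

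No other planned output fills the gap. RFS runs from the index date in all patients (Protocol section 3), not from remission in responders. The remission-free time in SAP 7.2 is not defined as a duration of remission either.

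At stake is a descriptive estimate that readers may set beside the median remission duration of 4.6 months quoted in the background of both documents. A plain summary could make remissions in this cohort look shorter because of the method alone.

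**Working it through.** The plan gives no DOR figure, event count or precision target, so there is no stated number to reproduce. The check is the size of the distortion once DOR runs from remission to relapse or death.

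**Inputs from the documents**
- Sample size 32 (protocol administrative change letter) and 81% response in the cited phase 3 trial: 32 × 0.81 = 25.9, about 26 responders.
- True median 4.6 months, from the same cited trial.
- InO started February 2017 to February 2022; data collected 13 February to 5 July 2023. Potential follow-up is about 12 to 77 months from InO start.

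**Assumptions (not in the documents)**
- 20% durable remissions and 20% loss to follow-up by 12 months.
- Administrative follow-up from remission uniform over 11 to 70 months.
- Exponential durations in patients without a durable remission.

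**Formulas**
1. Remission curve: S(t) = 0.20 + 0.80·exp(−λt). Setting S(4.6) = 0.50 gives exp(−4.6λ) = 0.30/0.80 = 0.375, so λ = 0.9808/4.6 = 0.2132 per month.
2. True upper quartile: exp(−λt) = (0.25 − 0.20)/0.80 = 0.0625, so t = 2.7726/0.2132 = 13.0 months.
3. Loss rate: γ = −ln(0.80)/12 = 0.0186 per month.
4. All times counted as finished: solve S(t)·exp(−γt) = 0.50 and 0.25. Before 11 months only loss censors. The solutions are 4.03 and 9.76 months.
5. Relapsers only: completed durations are close to exponential with rate λ + γ = 0.2318. The median is 0.6931/0.2318 = 2.99 and the upper quartile 1.3863/0.2318 = 5.98 months.

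**Simulation at the study's size** (26 responders, 4,000 replicates; about 27% of durations censored; repeat runs differ by a few tenths of a month)

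| Summary | Median (months) | Upper quartile (months) |
|---|---|---|
| Kaplan-Meier | about 4.6 | about 12.8 |
| All times counted as finished | 4.1 | 9.3 |
| Relapsers only | 3.0 | 5.7 |

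Against Kaplan-Meier, counting all times as finished lowers the median by (4.6 − 4.1)/4.6 = 11% and the upper quartile by (12.8 − 9.3)/12.8 = 27%. Using relapsers only lowers them by (4.6 − 3.0)/4.6 = 35% and (12.8 − 5.7)/12.8 = 55%.

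**Sensitivity to the assumptions**

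| Scenario | Kaplan-Meier | All times as finished | Relapsers only |
|---|---|---|---|
| 20% durable, no loss: median | true value 4.6 | about right | 3.2 |
| 20% durable, no loss: upper quartile | 12.7 | 11.7 | – |
| 20% durable, 10% loss: median | 4.45 | 4.3 | – |
| 20% durable, 20% loss, true median 9: median | 9.0 | 7.1 | 5.2 |
| 35% durable, 20% loss: upper quartile | not reached | 14.0 | 3.9 |
| No durable, no loss (large sample): median | 4.59 | 4.59 | 4.45 |
| No durable, 40% loss (large sample): median | 4.6 | 3.6 | 3.5 |

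In large samples neither plain summary exceeded the true median in any scenario where Kaplan-Meier could estimate it. The size runs from nothing to substantial.

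**The case against.** The strongest objection is that the SAP nowhere says ongoing remissions are dropped or cut short. A median and quartiles can be read off a Kaplan-Meier curve, and the wording does not exclude that. Protocol 9.7 also marks patients as censored in general terms before it names particular endpoints. This stands as far as it goes: a reader might infer that the plan orders deletion or truncation, and the documents do not support that. But nothing points to the Kaplan-Meier reading. Median and IQR is the protocol's default for any skewed quantity, DOR sits beside a count of transplants, and no rule says when a remission is censored.

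A reader might also take SAP section 6, "analysis will be on available data only", as an instruction to drop unfinished remissions. It is not. That section concerns missing values and imputation, a censored time is not a missing value, and the same rule covers OS, which gets Kaplan-Meier.

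Third, under SAP 5.1 as written, duration of remission is a time to response. Every responder then has a complete value, and a plain median loses nothing to censoring. That is correct, and it means the harm described here arises only once the definition is put right. It does not rescue item 7, because correcting the definition alone would leave an unsuitable summary in place.

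Finally, the study is descriptive, tests no hypothesis, and plans no formal comparison with the 4.6-month figure. With 26 responders, the 95% sampling range of the Kaplan-Meier median is about 2.2 to 9.3 months, far wider than a shortfall of half a month. This limits the importance of the point but does not remove it.

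**Conclusion.** The point holds in a limited form. An ordinary median and IQR is the stated summary for DOR in three places, DOR is on no Kaplan-Meier list, and the protocol itself expects censoring. For a duration from remission to relapse or death, that summary tends to understate DOR, mainly in the upper quartile.

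Under the assumed 20% durable remissions and 20% loss, the shortfall is about 0.5 months in the median and 3.5 months in the upper quartile if all times are kept, and 1.6 and 7.1 months if only relapsers are used. The relapsers-only figures are a possible outcome of the silence in the SAP, not something it prescribes.

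A reader might conclude that DOR will necessarily be understated. The documents do not support that: they give neither rate, and with no loss and all times kept the median is about right. The primary endpoint and the OS and RFS analyses are unaffected. The text should be corrected before analysis, but the point is not critical to the study.

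**What to change.** Make one edit that covers both the definition and the method:

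1. **SAP 5.1:** define DOR, in patients with CR/CRi, as the time from first documented CR/CRi to relapse or death, in place of the time to reach CR/CRi.
2. **SAP 7.2, 7.2.2 item 7 and section 8 item 7:** replace the plain median and IQR with Kaplan-Meier estimates of the median and quartiles with 95% confidence intervals, the number of events and the number censored. Censor patients without an event at the last date they were known to be in remission.
3. **Transplant and new therapy started in remission:** state how each enters the DOR analysis, consistent with the RFS definition in Protocol section 3, and add a sensitivity analysis that censors at transplant. This matters because 41% of InO patients in the cited trial went on to transplant.
4. **Kaplan-Meier lists:** add DOR in Protocol 9.7, SAP 7.1 and 7.2, and the SAP figure list.
5. **CRF:** confirm that it captures the date of first CR/CRi and the last date known to be in remission. The documents reviewed do not show this.

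The cost is a few lines of text and one more Kaplan-Meier run, provided the dates are on the CRF. Some quartiles may be reported as not reached, and intervals will be wide at a sample size of 32.

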#### List of figure

- 1. Kaplan-Meier curve for remission free survival
- 2. Kaplan-Meier curve for remission free survival stratified by the number of salvage therapies (0, 1, ≥2) received before InO initiation
- 3. Kaplan-Meier survival curve for overall survival

#### 7.2.3 Summary of Analyses

Not Applicable

#### 8 LIST OF TABLES AND TABLE SHELLS

- 1. The distribution of demographics characteristics (mean±SD for age and frequency and percentage for sex)
- 2. MRD Negativity following initiation of InO(frequency and percentage)
- 3. Dosage pattern(frequency and percentage)
- 4. Cause of death (frequency and percentage)
- 5. Occurrence of Grade 3/4 treatment-related adverse events in lung/cardiac/kidney/liver etc following InO initiation (frequency and percentage)
- 6. CR/CRi in EMD/LBL (frequency and percentage)
- 7. Duration of response(DOR) (Median and IQR)
- 8. No of patients who proceeded to transplant (Median and IQR)
- 9. Total during study treatment and post HSCT (Median and IQR)
- 10. Restricted remission free time with 95% confidence interval for both complete remission and complete remission with incomplete hematological recovery.
- 11. Restricted remission free time with 95% confidence interval for both complete remission and complete remission with incomplete hematological recovery stratified by the number of salvage therapies  $(0, 1, \ge 2)$  received before InO initiation
- 12. Restricted mean overall survival time with 95% CI.
- 13. Restricted relapse-free-survival with 95% CI for all patients and patients with or without follow-up HSCT

#### **APPENDICES**

Not applicable

8.1 APPENDIX 1: DATA DERIVATION DETAILS Not applicable A1.1 Definition and use of visit windows in reporting

None

#### A1.2 Further definition of endpoints

None

8.2 APPENDIX 2: ADDITIONAL STATISTICAL METHODOLOGY DETAILS None

#### A2.1 Further Details of the Statistical Methods

None

